8.4. REPORTING PROCEDURES

8.4.1. ADVERSE EVENT REPORTING

The investigator must document all AEs, ADEs, SADEs, UAE, UADEs and SAEs (see Section 8.1 for Definitions) on the AE Source Documents and subsequently enter this information into the electronic case report form, which will be reviewed by the study monitor and provided to the study sponsor. AE source documentation must be approved by the procedure-trained investigator.

8.4.2. SERIOUS ADVERSE EVENT REPORTING

The study investigator must report all SAEs and SADEs to the study sponsor immediately and without delay within 24 hours of site awareness and complete a AE CRF. See Section 1, Clinical Monitoring, for primary contact information.

All SAEs and SADEs will be followed until satisfactory resolution or until the site PI deems the event to be chronic or the adherence to be stable. Other supporting documentation of the event may be requested by the study sponsor and should be provided as soon as possible.

The study sponsor will be responsible for notifying FDA of SAEs pursuant to the MDR reporting requirements (21 CFR 803.19(a)(2)).

8.4.3. UNANTICIPATED PROBLEM REPORTING

An investigator shall submit to the sponsor and to the reviewing IRB a report of any Unanticipated Adverse Device Effect (UADE) occurring during an investigation as soon as possible, but no later than ten (10) working days after the investigator first learns of the effect (21 CFR 812.150(a)(1)).

A sponsor who conducts an evaluation of an unanticipated adverse device effect under 812.46(b) shall report the results of such evaluation to FDA pursuant to the MDR regulations and to all reviewing IRB's and participating investigators within ten (10) working days after the sponsor first receives notice of the effect.

8.5. STUDY HALTING RULES

Circumstances that may warrant termination or suspension include, but are not limited to the following unlikely events:

- Determination of unexpected, significant, or unacceptable risk to participants; or
- Insufficient compliance to protocol; or
- Determination that it is unlikely that the study null hypothesis can be rejected.

8.6. SAFETY OVERSIGHT

Adverse events will be reviewed periodically by the Medical Monitor. For any reported SAE, the Medical Monitor and Scientific Advisory Board members will review the relevant materials and may issue a recommendation to terminate the study as described above.

If this recommendation is reached, then the PI, study sites and IRBs will be notified. In addition, Spirox will follow the MDR reporting requirements pursuant to (21 CFR 803.19(a)(2)).

9. CLINICAL MONITORING

Clinical monitoring and oversight of the study will be conducted by the study sponsor, Spirox, to ensure that the safety, rights and well-being of human subjects are protected, that the reported trial data are accurate, complete, and verifiable, and that the conduct of the trial is in compliance with the currently approved protocol/amendment(s), with GCP, and with applicable regulatory requirement(s).

The clinical site monitoring plan for this study will utilize both on-site and centralized (remote) monitoring, with on-site visits occurring early in site enrollment and continuing throughout the study as deemed necessary. Data verification will consist of 100% Source Document Verification of primary and secondary endpoint data and adverse device effects through 6 months, verification of correct ICF execution, subject eligibility, and compliance with the protocol. Clinical monitoring for the remainder of the data collected includes CRF reviews for timing, completeness and consistency of the CRF data for each subject through study exit. Onsite visits are documented including letters to the site principal investigator for visit planning and for a summary of any visit observations.

An independent audit of Clinical Study File at Sponsor's site may be conducted during the course of the study.

10. STATISTICAL CONSIDERATIONS

10.1. STATISTICAL AND ANALYTICAL PLANS

A Statistical Analysis Plan (SAP) will be finalized prior to database lock, which will contain further analysis details and statistical methods.

All efficacy endpoints will be analyzed using data collected after the training cases are completed. The training cases will not be included in the efficacy endpoint analyses. The training cases will be summarized with descriptive statistics for information purposes only and will include a summary of adverse events.

The subjects that receive a replacement implant will be included in the modified Intention-to-Treat population but excluded from the per-protocol population. A separate sensitivity analysis will be conducted in which the subjects that received a replacement implant are considered non-responders.

10.2. STATISTICAL HYPOTHESES

Primary Efficacy Endpoint:

- The primary efficacy endpoint is the proportion of treatment responders at 6 months post procedure. Since there is no direct comparison group in this study, the primary efficacy hypothesis is a superiority comparison to a target proportion:

Null Hypothesis H_0 : the proportion of responders at 6 months is = 0.50, versus
Alternative Hypothesis H_A : the proportion of responders at 6 months is $\neq 0.50$

- There are no other formal statistical hypotheses.

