2.3.3. KNOWN POTENTIAL BENEFITS

The Latera™ Absorbable Nasal Implant is indicated to support upper and lower lateral nasal cartilage. The prior investigation described in Section 2.2, demonstrated that the device reduced nasal obstruction symptoms by 53.1 % at 12 months in patients with nasal valve collapse as a primary contributor to NAO (no septal or turbinate treatment). For subjects requiring lateral cartilage support that also have enlarged turbinates, it is expected that the Latera Implant may provide additional benefit as part of the overall treatment to alleviate NAO. In addition, subjects may benefit from the additional clinical monitoring and follow-up evaluations required by this study protocol.

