7.4. STANDARD OF CARE STUDY PROCEDURE

Per an Investigator's decision, subjects may receive concomitant turbinate reduction procedure(s) in addition to placement of the Implants to address other potential causes for the nasal airway obstruction.

There are two commonly used approaches to reduce turbinate size: radiofrequency reduction, and microdebrider-aided resection using a submucosal approach. With this procedure, the lining of the turbinate is left intact, but the tissue from the inside of the turbinate is removed. As the turbinate heals, it becomes smaller than before surgery.

The decision to perform turbinate reductions should be made based on the judgment of the investigator, but should consider the findings of the nasal exam as well as Assessment of Turbinate Hypertrophy Contribution to NAO (see sections 7.2.13 and 7.2.7). Investigators will be instructed to consider concomitant turbinate reductions for any subject for whom the results of these evaluations suggest that turbinate enlargement is contributing to nasal obstruction.

Turbinate reductions procedures are well established and considered standard of care to address respective etiologies. Treatment of the lateral wall with Latera alone or in conjunction with these procedures is being evaluated in this study.

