10.3. ANALYSES DATASETS

Four analysis populations will be considered: The analysis datasets described in the following section apply to the subjects enrolled in the main study (excluding training cases). The training subjects will not be included in the formal analyses for this protocol.

- Intention-to-Treat (ITT) Population: all enrolled subjects who began a nasal Implant procedure, regardless of concomitant turbinate treatment (i.e., Latera alone or in conjunction with turbinate treatment) or re-implant according to this protocol.
- Modified Intention-to-Treat (mITT) Population: all subjects enrolled who received at least one nasal Implant, regardless of concomitant turbinate treatment. Subjects that received a replacement implant will be included in this analysis dataset.
- Per-Protocol (PP) 6 Month Evaluable Population: subjects with 6 month post-Implant NOSE score assessments in clinic or by telephone, regardless of concomitant turbinate treatment. Subjects that received a replacement implant will not be included in this analysis dataset.
- Latera Stand-Alone Population: subjects who receive at least 1 Latera implant without concomitant turbinate treatment.

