10.4.2. ANALYSIS OF THE PRIMARY EFFICACY ENDPOINT(S)

The primary endpoint will be the proportion of treatment responders at 6 months post procedure. The mITT analysis dataset will be used to analyze the primary endpoint.

Responder is defined as a subject that has at least one (1) NOSE class improvement or at least 20% NOSE score reduction compared to baseline.

Subjects will be classified as non-responders if neither of these criteria is met.

NOSE score is a PRO instrument which measures the impact of nasal obstruction on quality of life. It is scored in increments of 5 points, and the total score is calculated as the sum of all 5 questions multiplied by 5, where the range is 0 (asymptomatic) to 100 (most extreme deleterious impact on quality of life). The NOSE score classes¹⁷ are based on the total calculated score:

- Mild:** 5 – 25 points
- Moderate:** 30 – 50 points
- Severe:** 55 – 75 points
- Extreme:** 80 – 100 points

This primary hypothesis will be evaluated for the mITT using a -2-sided exact test²³, and the corresponding exact (Clopper-Pearson) 2-sided 95% confidence interval will be calculated. The null hypothesis that the proportion of responders is $\neq 0.5$ will be rejected if the p-value is < 0.05 .

Sensitivity analyses will be conducted to determine the impact of missing data on these results. These analyses will depend on the extent of missing data, and will be detailed in the SAP, but may include:

1. Last observation carried forward (LOCF)
2. Subjects with missing data classified as non-responders
3. Re-implanted subjects classified as non-responders

This analysis will be repeated for the Latera stand-alone Population alone. While this study is not sufficiently powered to reject the null hypothesis for this subgroup, the response rate, 95% confidence interval and p-value will be calculated. See section 10.5 for further details.

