10.5. SAMPLE SIZE

The primary study hypothesis is a superiority comparison to a target proportion:

Null Hypothesis H_0 : the proportion of responders at 6 months is =0.50, versus
Alternative Hypothesis H_A : the proportion of responders at 6 months is $\neq 0.50$

See section 10.4.2 for the definition of response. This hypothesis will be evaluated using an exact test.

In order to have $> 90\%$ power to rule out a response rate $\leq 50\%$ at a 5% (2-sided) significance level, assuming a true response rate of 66%, 150 subjects with 6 month follow-up are needed. Assuming about 10% drop-out rate, up to 170 subjects will be enrolled. All mITT subjects will be used for this comparison, regardless of protocol deviations.

The assumed response rate is the minimum value is expected to be consistent with previous trials, where an 80% response rate at 6 months was observed.

The anticipated size of the Latera stand-alone Population is 50 subjects. With only 50 subjects in this cohort, the power to reject the primary null hypothesis is approximately 63%, given a true response rate of 66%. Although this cohort is not sufficiently powered to show significance for a true response rate of 66%, the p-value and exact binomial 95% confidence interval will be calculated for this population. Retrospective power for the actual response rate will also be calculated for this comparison in order to contextualize the results.

Sample size calculations were performed using the package RCT Design for R version 3.2.3.

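### The only formal test pools Latera alone with Latera plus turbinate reduction, so a positive result cannot by itself support a claim for Latera alone; the planned stand-alone test should be gated behind it.

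*Combined protocol and SAP*

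**What the plan says.** The objective (Section 3) covers Latera placed with or without concurrent turbinate reduction. Section 7.4 treats turbinate reduction as an established treatment of nasal obstruction, leaves its use to the investigator's judgement, and states: "Treatment of the lateral wall with Latera alone or in conjunction with these procedures is being evaluated in this study".

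Section 10.2 sets the null as "the proportion of responders at 6 months is = 0.50" and closes with "There are no other formal statistical hypotheses". Section 10.4.2 tests this with a two-sided exact test in the mITT population, which Section 10.3 defines as "all subjects enrolled who received at least one nasal Implant, regardless of concomitant turbinate treatment".

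The Protocol Summary commits to at least 50 stand-alone subjects, Section 10.3 defines a Latera Stand-Alone Population, and Section 10.4.2 repeats the primary analysis there with a rate, confidence interval and p-value, while saying that "this study is not sufficiently powered to reject the null hypothesis for this subgroup". Section 10.5 puts its power at about 63% with 50 subjects and a true rate of 66%. Section 10.4.9 makes no type I error adjustment and treats everything except the primary endpoint as supportive.

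**The concern.** The protocol says it evaluates the implant both alone and in combination, and it reserves subjects for the first question. Yet the only test with type I error control answers the mixed question. Turbinate reduction treats the same symptom, so the mixture can exceed 50% because of the combined-treatment subjects even if implant-alone subjects only meet the target. The stand-alone p-value has no place in the hypotheses and no testing order.

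Appendix II says the data may support regulatory applications and publications. At stake is which claim a positive primary result can carry, and whether any formal claim for Latera alone will be possible.

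**Working it through.** **Inputs.** From Sections 10.2, 10.4.2 and 10.5: null 0.50; two-sided alpha 0.05; exact binomial test; 150 evaluable subjects; overall rate 66%; about 10% drop-out; 50 anticipated stand-alone subjects. Assumed: 100 of the 150 evaluable subjects had combined treatment (150 − 50). The combined-group rate is not given, so a range of 60% to 80% is shown.

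**1. The plan's own power figures.** The rejection limit is the smallest k with 2·P(X ≥ k | n, 0.5) ≤ 0.05. Power is P(X ≥ k | n, 0.66).

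- n = 150: k = 88, two-sided size 0.0409, power 97.5%. The stated power above 90% is met.
- n = 50: k = 33, two-sided size 0.0328, power 56.5%. The stated 63% is not reproduced by the exact test.
- n = 50, normal approximation: Φ[(0.16·√50 − 1.96·0.5) / √(0.66·0.34)] = Φ[(1.131 − 0.980)/0.474] = Φ(0.32) = 62.5%. The stated figure matches this approximation, not the test the plan names.
- With 10% drop-out the stand-alone group falls to 45: k = 30, exact power 53.2%.

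**2. Pooled success when stand-alone response is exactly 50%.** With X₁ ~ Bin(50, 0.50) and X₂ ~ Bin(100, p), success is P(X₁ + X₂ ≥ 88), by exact convolution. The pooled rate is (25 + 100p)/150.

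| Combined-group rate p (assumed) | Pooled rate | Probability the primary test succeeds |
|---|---|---|
| 60% | 56.7% | 34.1% |
| 66% | 60.7% | 72.4% |
| 70% | 63.3% | 90.2% |
| 74% | 66.0% | 97.8% |
| 80% | 70.0% | 99.9% |

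The 74% row is the one that reproduces the plan's overall 66%: (0.66·150 − 0.50·50)/100 = 0.74. The group split matters too. The Protocol Summary's minimum of 50 allows more stand-alone subjects; with 75 and 75, and p = 74%, the pooled rate is (37.5 + 55.5)/150 = 62.0% and success falls to 83.0%.

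**3. Exact stand-alone power at fixed true rates.**

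| True stand-alone rate | n = 50 (33 or more) | n = 45 (30 or more) |
|---|---|---|
| 66% | 56.5% | 53.2% |
| 70% | 78.2% | 74.6% |
| 74% | 92.3% | 89.9% |
| 80% | 99.4% | 98.9% |

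**4. Error control under a fixed sequence.** The mITT test keeps its full 0.05, and the familywise error stays at or below 5%. If the true stand-alone rate is 50%, the chance of a false positive claim for Latera alone is at most P(X ≥ 33 | 50, 0.5) = 1.64%. With a combined-group rate of 66% or more, both steps succeed with probability about 56% at a stand-alone rate of 66%, 78% at 70%, and 99% at 80%.

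**The case against.** **Pooling is the declared objective, so nothing is contradictory.** This stands. A reader might infer that the mITT test is invalid or aimed at the wrong population; Section 3 does not support that. The point concerns only the reach of the claim.

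**Most of the remedy is already there.** The population, subject numbers, exact test, interval and p-value are planned, and 10.4.9 advises caution. With 25 responders out of 50, the planned interval would run from about 36% to 64%, so a weak stand-alone result would be visible. This stands as well. What is missing is a prespecified place for that p-value, without which it cannot support an error-controlled claim.

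**The alarming probability is conditional.** A reader might infer that the primary test is about 98% certain to succeed when the implant alone only meets the target. That needs a back-solved 74% combined-group rate and a one-third stand-alone share. A stand-alone rate of 50% is itself a stress case that the plan does not expect.

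**Low stand-alone power is a fair statement.** At 66% it is correct. A reader might dismiss it because Section 10.5 cites earlier trials "where an 80% response rate at 6 months was observed", and the one prior study described (Sections 2.2 and 2.3.3) involved no septal or turbinate treatment. But the documents do not say that the 80% comes from that study. If it were 24 of its 30 subjects, the exact 95% interval would be about 61% to 92%, which includes 66%.

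**A gated p-value does not isolate a device effect.** Correct. The study is open label and single arm, and investigators choose who has turbinate reduction. Step 2 controls error only against the fixed 50% target in a selected group.

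**Conclusion.** The concern holds as a limit on what the primary result can show, and the change is worth making. If stand-alone response were only 50%, the pooled test would still succeed with probability between 34% and 99.9% for combined-group rates from 60% to 80%, assuming 50 stand-alone and 100 combined evaluable subjects. These are conditional stress-case figures, not forecasts. A claim for Latera with or without turbinate reduction follows from the primary test; a formal claim for Latera alone does not.

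The description of the stand-alone test as underpowered is right at the design rate and should be qualified rather than removed. The 63% attached to it is too high for the named exact test.

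**What to change.** 1. In 10.2 and 10.4.9, add a fixed sequence: first the mITT test as planned; then, only if it rejects above 0.50, the same exact test in the Latera Stand-Alone Population at two-sided 0.05.
2. Fix this before any outcome data are aggregated or reviewed. The study is open label, and 10.4.7.1 allows NOSE changes to be aggregated before database lock, so a later addition would not be credible as prespecified.
3. State that step 1 supports only a claim for Latera with or without turbinate reduction, and that a formal claim for Latera alone needs step 2.
4. In 10.4.2 and 10.5, keep the statement that power is low at 66%. Replace 63% with the exact 56.5% (n = 50) and 53.2% (n = 45), and add power at other fixed rates: with n = 50, 78% at 70%, 92% at 74% and 99% at 80%.

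Cost: wording in the protocol and SAP, subject to the timing condition, with no extra subjects and no alpha taken from the primary test. The downside is that a stand-alone miss becomes a formal miss. At a true rate of 66% that happens about 43.5% of the time with 50 subjects (100 − 56.5) and 46.8% with 45 (100 − 53.2). The primary result is unaffected either way.

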10.3. ANALYSES DATASETS

Four analysis populations will be considered: The analysis datasets described in the following section apply to the subjects enrolled in the main study (excluding training cases). The training subjects will not be included in the formal analyses for this protocol.

- Intention-to-Treat (ITT) Population: all enrolled subjects who began a nasal Implant procedure, regardless of concomitant turbinate treatment (i.e., Latera alone or in conjunction with turbinate treatment) or re-implant according to this protocol.
- Modified Intention-to-Treat (mITT) Population: all subjects enrolled who received at least one nasal Implant, regardless of concomitant turbinate treatment. Subjects that received a replacement implant will be included in this analysis dataset.
- Per-Protocol (PP) 6 Month Evaluable Population: subjects with 6 month post-Implant NOSE score assessments in clinic or by telephone, regardless of concomitant turbinate treatment. Subjects that received a replacement implant will not be included in this analysis dataset.
- Latera Stand-Alone Population: subjects who receive at least 1 Latera implant without concomitant turbinate treatment.

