4.2. STUDY ENDPOINTS

4.2.1. PRIMARY ENDPOINTS

Primary Efficacy Endpoint: Proportion of treatment responders at 6 months post procedure.

- A responder is defined as a subject that has at least 1 NOSE class improvement or at least 20% NOSE score reduction.

Primary Safety Endpoint: Nasal procedure and Latera device-related adverse events through 6 months.

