7.1. STUDY VISIT SPECIFIC PROCEDURES

7.1.1. Subject Screening and Enrollment Visit (Visit 1) (All Subjects)

All subjects seeking treatment for nasal obstruction will be screened for eligibility according to the inclusion/exclusion criteria. A member of the research team will review the subject's medical history for eligibility and inclusion into the study.

The subject will be asked to fill out a NOSE score questionnaire and a NOSE score will be calculated. If all inclusion criteria (including NOSE score ≥ 55) are met and no exclusion criteria are present, the Investigator will inform the subject about the purpose of the study. The background of the proposed study along with the potential benefits and risks will be explained to the subject and questions will be answered. Potential subjects will be counseled as to the nature of their condition. All subjects will have ample time to ask questions.

Subjects indicating that they would like to proceed with study participation, and who are willing to comply with the requirements of the study protocol, will be asked to sign an Informed Consent Form (ICF) that has been approved by the governing IRB. Failure to provide written informed consent renders the subject ineligible for the study.

Female subjects of childbearing potential will undergo a pregnancy test to verify eligibility. Women of childbearing potential are defined as any female who has experienced menarche and who is NOT permanently sterile or postmenopausal. Postmenopausal is defined as twelve (12) consecutive months with no menses without an alternative medical cause.

Subjects that have signed the ICF and met eligibility criteria will be scheduled for Visit 2. Subjects will be considered enrolled upon signing the ICF, meeting study eligibility criteria, at the completion of the screening visit.

Study data including any adverse events that occurred after the ICF was signed, should be entered into the EDC within 24 hours of completion of the visit.

Subjects that have provided written informed consent and met the eligibility criteria may also be invited to participate in "Latera™ Patient Experience and Testimonials" (see Section 7.2.16 below).

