7.1.3. Treatment Visit (Visit 3) (All Subjects)

This visit may be completed in conjunction with Visits 1 and 2, and should take place within 1 month after Visit 1 (Screening & Enrollment Visit). This visit is completed by all subjects.

If treatment occurs more than 1 month after Visit 1, inclusion and exclusion criteria must be re-confirmed and the subject will be asked to re-review, initial and date the ICF to continue participation. Subjects will also complete a NOSE scale.

Procedures conducted under this study protocol must be completed in an office setting using sterile technique. In addition to local anesthesia, subjects may receive monitored anesthesia care (MAC) or conscious sedation per the site's standard of care practice. Only procedure-trained investigators that are authorized by the sponsor will be allowed to place the devices during this study.

Optionally, an oral anxiolytics (e.g. Valium, Ativan or equivalent) and/or analgesic (e.g. Tylenol, or Tylenol with Hydrocodone) may be offered to the subject prior to the procedure, per the investigator's discretion.

If the subject has agreed to provide a testimonial (see Section 7.2.16), video may be captured during the procedure visit.

The below section includes a description of the activities occurring during the Index procedure visit and placement of the Latera™ Implants:

1. Amoxicillin or equivalent antibiotic may be administered to the subject before the procedure.
2. If planned treatment includes turbinate reduction, it must be completed prior to implant placement per site's standard of care procedure.
3. The skin of the nose and the mucosal surface should be cleaned with an antiseptic solution (e.g. isopropyl alcohol or betadine ophthalmic) prior to Latera Implant(s) placement.
4. The nasal anatomy will be examined and target trajectory for the Implant(s) should be established and marked with the aid of a sterile pen and sterile implant positioning guide per IFU (**Appendix III**).
5. Images of planned placements will be captured.
6. The following local anesthesia steps may be considered per site's standard of care procedures to ensure subject comfort during implant placement.
 - a. SPRAY: Anesthetic (e.g. Lidocaine or equivalent) or decongestant (e.g. Afrin or equivalent) may be sprayed into the nose.

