10.4.4. SAFETY ANALYSES

Two analysis sets will be used to summarize adverse events. The ITT analysis set will be used to summarize acute adverse events (through 1 month post procedure), and the mITT analysis set will be used to summarize adverse events over the entire duration of follow-up. The primary safety reporting time-point is 6 months post-implant.

The overall incidence (i.e., number and percent of subjects with 1 or more adverse event) of adverse events, serious adverse device events, serious adverse events, fatal adverse events, and device related events (e.g., possibly, probably or definitely related) will be calculated for the acute phase, through 6 months post-procedure and for the entire duration of follow-up. The overall incidence of mild, moderate and severe events will be calculated by considering the most severe event for each subject.

In addition, the overall incidence for each adverse event type will be calculated. The adverse event types will be classified as defined in section 8.1.1

The implant retrieval rate will be calculated based on the number of implants retrievals per the total number of implants placed.

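### The two adverse event analysis sets are tied to the implant step, so a subject whose visit is stopped by harm at the earlier turbinate step is missing from the 6-month safety summary and, on the natural reading, from every analysis set

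*Combined protocol and SAP*

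**What the plan says.** Section 10.3 defines four analysis sets for the main study:

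- ITT: "all enrolled subjects who began a nasal Implant procedure, regardless of concomitant turbinate treatment".
- mITT: "all subjects enrolled who received at least one nasal Implant".
- Per-protocol: "subjects with 6 month post-Implant NOSE score assessments in clinic or by telephone".
- Stand-alone: "subjects who receive at least 1 Latera implant without concomitant turbinate treatment".

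Section 10.4.4 assigns two of these to safety. ITT serves the acute phase, up to 1 month, and mITT serves the full follow-up. Incidence is to be reported for the acute phase, through 6 months and overall. The 6-month point, counted from the implant, is the primary one. The primary safety endpoint in section 4.2.1 is "Nasal procedure and Latera device-related adverse events through 6 months", so it covers procedural as well as device harm.

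On the order of steps, section 7.1.3 states: "If planned treatment includes turbinate reduction, it must be completed prior to implant placement". Enrollment is complete at the end of the screening visit (section 7.1.1), before any treatment.

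**The concern.** Entry to every set depends on starting the implant procedure, or on receiving an implant. In a combined case, another procedure comes first. If that procedure goes wrong and the visit ends there, the subject may never meet the entry condition of any set used for safety.

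Such an omission would not be random. The subject leaves the denominator because of the event that the table is meant to count, and this favours a lower reported rate. The study objective (section 3) covers office treatment with or without turbinate reduction, and section 2.3.2 lists bleeding that needs further intervention among the turbinate risks. The scenario therefore comes from the protocol's own risk section.

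**Working it through.** This is mainly a reading of the text. The plan states no figure on this point, so there is none to reproduce.

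**Step 1. Is the subject enrolled?** Yes. Enrollment is complete at the end of screening (7.1.1), and adverse events are recorded from consent: "Study data including any adverse events that occurred after the ICF was signed".

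**Step 2. Is turbinate reduction part of the implant procedure?** Four places treat it as separate:
- 7.5 says that the implant procedure may be done together with it.
- 7.1.6 applies the implant procedure of 7.1.3 to re-implantation with concomitant procedures left out.
- 8.2.2 gives turbinate-related events their own relationship category.
- 10.3 itself calls the turbinate treatment concomitant.

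Against this, 7.1.3 lists turbinate reduction as step 2 of a single numbered sequence for the visit. No section says when the implant procedure begins.

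**Step 3. Where does each stopped visit fall?**

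| Visit stopped | Acute table (ITT) | 6-month summary (apparently mITT) |
|---|---|---|
| At the turbinate step, or by sedation or anesthesia given for it; natural reading | out | out |
| Same, if every numbered step of 7.1.3 counts as the implant procedure | in | out |
| After anesthesia for implant placement (7.1.3, step 6), no implant placed | arguably in | out |
| After an implant was placed | in | in |

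The right-hand column holds whatever starting the procedure means, because mITT needs an implant. It rests on one inference: 10.4.4 names no set for the 6-month window, and that window runs past the month for which ITT is assigned.

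**Step 4. How much could it matter?** The documents give no rate of visits stopped before the implant step. Let k be the number of omitted subjects, each with an event. Assume that all 170 main-study subjects (the ceiling in 10.5) had some study procedure started and that only these k are omitted. They are already enrolled, so they lie within the 170. The table as planned shows e/(170 − k), and the complete table shows (e + k)/170, where e is the number of subjects with an event among those retained. Intervals are Clopper-Pearson 95%.

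| e (assumed) | k (assumed) | As planned | Complete |
|---|---|---|---|
| 0 | 1 | 0/169 = 0% (0 to 2.2%) | 1/170 = 0.6% (0.01 to 3.2%) |
| 0 | 3 | 0/167 = 0% (0 to 2.2%) | 3/170 = 1.8% (0.4 to 5.1%) |
| 17 | 1 | 17/169 = 10.1% | 18/170 = 10.6% |
| 17 | 3 | 17/167 = 10.2% | 20/170 = 11.8% |

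For a common event the shift is 0.5 to 1.6 percentage points. For a rare serious event it is the difference between none and some.

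**The case against.** The strongest reply is that the ITT definition turns on an undefined word. Section 7.1.3 gives one numbered sequence, and turbinate reduction must precede implant placement, which need not mean that it precedes the implant procedure. ITT applies whatever turbinate treatment was given, and its contrast with mITT suggests that it was meant to keep stopped procedures. On that view the subject is in ITT. This is a fair reading, although 7.1.6, 7.5 and 8.2.2 weigh against it. It rescues only the acute table, because mITT still leaves the subject out at 6 months.

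A reader might go further and infer that anyone harmed by anesthesia, including a stand-alone subject, falls outside every set. The documents do not support this. Step 6 of 7.1.3 gives local anesthesia for comfort during implant placement, including along the implant track. Such a subject has arguably begun the implant procedure and belongs in the acute table. For monitored care or sedation that is not tied to either step, the text leaves the matter open.

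A reader might also infer that these events are lost, or survive only in the optional listing of 10.4.10. That is too strong. Treatment-visit events are documented (7.1.3) and captured on case report forms (8.3). The Medical Monitor reviews adverse events, and Scientific Advisory Board members join the review of serious ones (8.6). What is missing is a place in the planned summary tables.

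Finally, section 10.1 leaves further detail to a SAP that is to be final before database lock, and the point could be settled there. It should be, but the sets are already defined in 10.3, and a choice made after events are known would be open to question.

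**Conclusion.** The concern holds in a limited form. A main-study subject who is stopped at the turbinate step is in no analysis set on the natural reading. On the broad reading the subject is in the acute ITT table only. On either reading the 6-month primary safety summary appears to leave out this subject, along with any ITT subject who began the implant procedure but received no implant.

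This rests on 10.4.4 using mITT at 6 months, which it implies but does not say outright. The number affected is unknown and probably small. Section 2.3.2 describes perioperative adverse events as infrequent for septoplasty and turbinate surgery. The values of k and e above are illustrations, not estimates. The effect on common event rates is minor. The weight of the point lies in rare serious procedural events, and in the fact that exclusion depends on the harm itself. The efficacy analysis and the power calculation are not affected.

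**What to change.** In sections 10.3 and 10.4.4:

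1. Define a safety set of all enrolled main-study subjects in whom any study procedure at Visit 3 was started: sedation or anesthesia, turbinate reduction, or implant.
2. Count time from Visit 3, which section 10.4.1 already makes Day 1, so that the 6-month window exists for a subject without an implant.
3. Use this set for the acute and the 6-month adverse event tables, and report how many of its subjects had no implant placed.
4. Keep mITT as the denominator for device-related incidence, so that subjects without an implant do not dilute it.
5. Leave the efficacy sets as they are.

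The cost is a sentence or two of text and one more denominator to report. Procedure-related rates may look slightly less favourable. No new data are needed, since the events are already collected.
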